5.4.6 Laboratory Evaluations

Continuous laboratory parameters (serum chemistry, hematology, coagulation (only at screening after amendment 3 and for those patients receiving anti-coagulation), urinalysis, urinalysis [microscopic]) listed in Table 4; fasting serum glucose, and HbA1c will be summarized using descriptive statistics for the observed value and the change from baseline by history of diabetics. Missing values for any of the laboratory evaluations will not be imputed; that is, only observed case data will be used. Baseline is defined as the last value prior to the first dose of study medication. Categorical urinalysis data will be listed, but will not be summarized.

As part of the AESI evaluation, below safety lab abnormality will be summarized by treatment group. All post-baseline lab values are being considered. Further details are provided in Section 5.4.6.1 through 5.4.6.4.

- ALT or AST (> 3x ULN and >5xULN)
- TB (> 2x ULN)
- Potential Hy's Law case: (ALT and/or AST > 3xULN with concurrent TB > 2xULN)
- CK (> 5x ULN) and (>10x ULN)
- Fasting Serum Glucose (mg/dL) (≤ 50 , and ≥ 126) by history of diabetics
- HbA1C ($\geq 6.5\%$) by history of diabetics
- Creatinine (change from baseline for >1 mg/dL)
- eGFR (< 15 mL/min/1.73m², 15 < 30 mL/min/1.73m²)
- Hgb (g/dL) (decrease from baseline for ≥ 2 g/dL)
- Hgb (<8 g/dL)

Table 4: Clinical Laboratory Parameters (Safety)

Hematology 
 • Hematocrit (Hct) • Hemoglobin (Hgb) • Mean corpuscular hemoglobin (MCH) • Mean corpuscular hemoglobin concentration (MCHC) • Mean corpuscular volume (MCV) • Platelet count • Red blood (RBC) cell count • White blood (WBC) cell count with differential (absolute and %) 	Blood Chemistry (serum, fasting) 
 • Albumin (Alb) • Alkaline phosphatase (Alk-P) • Alanine aminotransferase (ALT; SGPT) • Aspartate aminotransferase (AST; SGOT) • Blood urea nitrogen (BUN) • Calcium (Ca) • Carbon dioxide (CO₂) • Chloride (Cl) • Creatinine • Creatine kinase (CK) • Glucose • Lactate dehydrogenase (LDH) • Phosphorus • Potassium (K) • Sodium (Na) • Total and direct bilirubin (TB) • Total protein • Uric acid
Urinalysis (Dipstick) 
 • Clarity • Bilirubin • Color • Glucose • Ketones • Leukocyte esterase • Nitrate • Occult blood • pH • Protein • Specific gravity • Urobilinogen 	Coagulation (In all patients at screening, then only in patients receiving anticoagulant therapy that in the investigator's judgment require monitoring at Visit T1 and 3 to 5 days post Visit T1) 
 • Prothrombin time (PT) • International normalized ration (INR)
Urinalysis (Microscopic)-only if urine dipstick abnormal 
 • Bacteria • Casts • Crystals • Epithelial cells • Red blood cell (RBC) • WBC 	

The number and percentage of patients with laboratory abnormalities (i.e., laboratory values outside the stated laboratory normal range) will be summarized at each time point (i.e., including baseline and post-baseline time points) for each laboratory parameter. The determination of laboratory abnormalities will take into account any unscheduled laboratory assessments. Additional lab-related summaries will be provided as follows for hepatic safety, musculoskeletal safety, diabetes and glycemia, and renal safety.

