#### Renal Safety

Baseline estimated glomerular filtration rate (eGFR) will be summarized by treatment group for actual value and for baseline eGFR categories. Shift tables of eGFR category from baseline over the study, will be provided by treatment group. Shift tables of urine protein (negative/positive) from baseline over the study, will be provided by treatment group. Values of CK over the study will be summarized by treatment group and by baseline eGFR category. Finally, muscle-related AEs will be summarized by treatment group and by baseline eGFR category.

Clinical Endpoints

*Clinical endpoints* will be monitored and adjudicated by an independent blinded expert CEC for ongoing studies the ETC-1002 program. Adjudicated *clinical endpoints* will be summarized by event type and treatment group. Additional details regarding *clinical endpoints* and *clinical endpoint* definitions will be included in CEC charter.

Neurocognitive Events

Neurocognitive events will be identified and evaluated by routine safety monitoring of PE findings and AEs. Summarization of neurocognitive events will occur using prespecified Medical Dictionary for Regulatory Activities (MedDRA) terms and will be performed by SOC, severity, and relationship to study drug for each treatment group

Key Efficacy Endpoints

*Percent change from baseline to Week 12 or Week 24 in LDL-C, non-HDL-C, TC, apoB, and hs-CRP will be analyzed using analysis of covariance (ANCOVA), with treatment and randomization strata (patient's CV risk and baseline statin dose) as factors and respective baseline value as a covariate. The FAS will be used. Missing data for these endpoints will be imputed using multiple imputation taking account for treatment adherence.*

Other Efficacy Endpoints

*LDL-C, HDL-C, TG, TC, non-HDL-C, hs-CRP, and apoB values at other time points will be summarized and analyzed similarly to the key lipid endpoints. In addition, a summary using the FAS, excluding patients who received additional lipid-lowering therapy by that time point (by Week 24 for the Week 24 time point; by Week 52 for the Week 52 time point), will be provided. For both summaries, only observed case data will be used (no imputation for missing data).*

Additional post-randomization adjunctive lipid-modifying therapy

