4.6 Changes from Protocol Planned Analyses

- 1) Additional subgroup analysis and sensitivity analyses are proposed and described in this SAP.
- 2) It is clarified in the SAP that study objectives are supported by both primary safety and primary efficacy endpoints.
- 3) Multiplicity adjustment amongst efficacy endpoints is implemented and described in this SAP.

5 Statistical and Analytical Plans

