5.4.3 Muscle Related Adverse Events

Muscle related adverse events as reported on the general AE CRF will be summarized by SOC, PT, and maximum severity. All muscle related events and details associated with it including cause and location will be provided in a listing.

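### Two safety tables planned in the protocol, urine protein shifts by arm and muscle-related events by baseline eGFR, are missing from the SAP, and neither departure is declared

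*SAP*

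**What the plan says.** The protocol synopsis, in the Renal Safety paragraph of its statistical methods, makes three commitments that matter here:

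- Urine protein: "Shift tables of urine protein (negative/positive) from baseline over the study, will be provided by treatment group".
- CK: "Values of CK over the study will be summarized by treatment group and by baseline eGFR category".
- Muscle-related events: "Finally, muscle-related AEs will be summarized by treatment group and by baseline eGFR category".

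The SAP handles these topics as follows.

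- **Urinalysis.** SAP 5.4.6 states "Categorical urinalysis data will be listed, but will not be summarized". Later in the same section it says that counts and percentages of patients outside the normal range "will be summarized at each time point (i.e., including baseline and post-baseline time points) for each laboratory parameter". Dipstick protein is one of the parameters in the SAP's Table 4.
- **Renal safety.** SAP 5.4.6.4 contains eGFR summaries and shifts and a creatinine/eGFR abnormality table. It has no urine protein output.
- **Muscle-related events.** Under SAP 5.4.3 these "will be summarized by SOC, PT, and maximum severity". Baseline eGFR is not mentioned.
- **CK.** SAP 5.4.6.2 keeps the split by baseline eGFR category.

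SAP section 2 and protocol 12.1 both say that the SAP prevails where the two differ on analysis.

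**The concern.** General safety is the primary endpoint, and the SAP's list of events of special interest has both a muscular and a renal group. Patients enter with eGFR as low as 30 on a background statin. The protocol also treats renal function and statin exposure together in one eligibility note: it excludes patients on simvastatin 40 mg whose eGFR is below 45. Whether muscle-related events concentrate in patients with reduced renal function is therefore a question that the sponsor raised itself.

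Because the SAP prevails, anyone programming from it would produce neither table, and nothing would record that this was a decision. CK by baseline eGFR is kept while muscle-related events by baseline eGFR are not, although both come from the same protocol paragraph. With no reason given, that looks like an oversight.

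**Working it through.** No sample size, power or event figure is involved. The check sets the five outputs of the protocol's Renal Safety paragraph against the SAP.

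| Protocol output (synopsis, Renal Safety) | Where in the SAP | Kept? |
|---|---|---|
| Baseline eGFR, value and category | 5.2.4 (category) | Yes |
| eGFR category shift tables by arm | 5.4.6.4 | Yes |
| Urine protein negative/positive shift by arm | None: listing rule in 5.4.6, nothing in 5.4.6.4 | No |
| CK by arm and baseline eGFR | 5.4.6.2 | Yes |
| Muscle-related events by arm and baseline eGFR | None: 5.4.3 has no eGFR split | No |

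Three of five are kept and two are absent.

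**Could another section produce the missing tables?** SAP 5.4.1 repeats the event tables, including those for events of special interest, for the subgroups in 5.2.5. That section names nine variables: gender, age, CV risk category, statin intensity, race, baseline LDL (efficacy only), diabetes history, BMI and region. Baseline eGFR is not among them, so this route does not give muscle-related events by renal function. For urine protein, the only candidate is the general abnormality count in 5.4.6.

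**Would that count replace a shift table?** Take the patients with results at both baseline and a given visit. Let a be the number who go from negative to positive and b the number who go from positive to negative. Then

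abnormal at visit − abnormal at baseline = a − b.

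The two counts give only the net difference. The number with new proteinuria, a, cannot be recovered from them. The shift table reports a and b separately for each arm.

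**Is the departure declared?** SAP 4.6 lists three changes from the protocol: "Additional subgroup analysis and sensitivity analyses are proposed and described in this SAP", a clarification about objectives and endpoints, and the multiplicity procedure. None of the three concerns these tables. The summary of changes at the end of the SAP has 16 items. The nearest is item 15, on special-interest terms and laboratory cut-offs, and it mentions neither table. The tally is 0 of 3 and 0 of 16.

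**Are the data available?** Urinalysis is collected at the scheduled clinic visits (protocol Appendix 1), and protein is on the dipstick panel (protocol Table 5). Muscle-related events are assessed at each post-baseline visit, and baseline eGFR categories are already defined in SAP 5.2.4. Nothing new has to be collected.

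**The case against.** The case on the other side has real substance, and it rules out several stronger readings.

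- **A reader might infer that an imbalance in proteinuria could not be seen at all.** The documents do not support that. If the abnormality-count sentence in 5.4.6 prevails over the listing rule, abnormal urine protein is tabulated by time point. The SAP contradicts itself here; it does not plainly drop all tabulation. What is certainly missing is the cross-tabulation of baseline against later values.
- **A reader might infer that renal injury is then watched only through creatinine and BUN.** It is not. eGFR is summarized and shifted, and the dipstick includes occult blood, with casts and red cells on microscopy when the dipstick is abnormal.
- **A reader might infer that muscle safety in renal impairment goes unexamined.** CK by visit and baseline eGFR category is kept. Muscular events of special interest, including myalgia, myopathy and rhabdomyolysis, are tabulated by age, diabetes and statin intensity. SAP 5.4.4 and 5.4.6.2 add event and CK summaries for patients on simvastatin 40 mg or more. One cross-tabulation is missing, not surveillance as such.
- **A reader might infer concealment.** The listing rule is stated openly, and the precedence of the SAP is declared. The accurate statement is that neither departure is listed or given a reason.
- **A reader might want a power figure for a proteinuria difference.** The documents give no proteinuria rates, and SAP 5.4 plans descriptive safety summaries, so a restored table would carry no test.

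It is also fair to say that protocol 12.5 is partly redacted, so the comparison rests on the synopsis. The synopsis is current protocol text, however, and the commitments in it are explicit. None of these points supplies either missing table.

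**Conclusion.** The point holds as a gap between protocol and SAP. Two of the five outputs in the protocol's Renal Safety paragraph have no counterpart in the governing SAP, and neither omission is declared. SAP 5.4.6 also contradicts itself on whether urine protein is tabulated. The consequence is moderate: two planned descriptive outputs for the primary safety endpoint are lost, but no test, estimate or error rate is affected. The conclusion assumes that dipstick protein counts as categorical urinalysis, which the protocol's own negative/positive coding supports, and that the redacted part of protocol 12.5 does not withdraw what the synopsis plans.

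**What to change.** 1. In SAP 5.4.6, reconcile the listing-only rule for categorical urinalysis with the promise of abnormality counts for every laboratory parameter. State which applies to dipstick protein.
2. In SAP 5.4.6.4, restore the negative/positive urine protein shift table from baseline by treatment group, using the laboratory baseline already defined in 5.4.6.
3. In SAP 5.4.3, add muscle-related adverse events by treatment group and baseline eGFR category, using the categories in 5.2.4.
4. If either table is left out on purpose, list it in SAP 4.6 with the reason.

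The cost is two descriptive tables and a few sentences of SAP text. No new data, visits or tests are needed.

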3.2 Primary Safety Endpoints

The primary safety endpoint for this study is general safety, which includes adverse events (AEs), clinical safety laboratories, physical examinations (PEs), vital signs, and electrocardiogram (ECGs).

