3.2.1 Adverse Events

The evaluation of AEs will include only incidence of treatment-emergent AEs (TEAEs), defined as AEs that begin or worsen after the first dose of IMP until 30 days after last dose of IMP. Clinical endpoints will be collected and adjudicated by an independent

Confidential

Page 7 of 33

Clinical Events Committee (CEC). Clinical endpoints will also be reported as SAEs. Adverse events of special interest (AESI) will further be examined (See Section 5.4.2 for more information).

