3.2.2 Clinical Safety Laboratories

The evaluation of clinical safety laboratories, including blood hematology, chemistry, coagulation, and urinalysis, will be based on the observed values. Observed values and changes from baseline will be summarized for all post-baseline study visits.

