Route of Administration:	Oral, daily (once every 24 hours, at approximately the same time each day), with or without food	Oral, daily (once every 24 hours, at approximately the same time each day), with or without food
Physical Description:	Oval, white to off-white film-coated tablet debossed with “ABC” on one face and debossed with “000” on the opposite face	Oval, white to off-white film-coated tablet debossed with “ABC” on one face and debossed with “000” on the opposite face
Manufacturer (Fill/Finish):	Norwich Pharma Services [name] AND: Patheon [name]	Norwich Pharma Services [name] AND: Patheon [name]

^a A 100-day supply of IMP will be included in the 100-count bottle and a 35-day supply of IMP will be included in the 35-count bottle.

Randomized patients will continue in the study until they have completed Week 52 (Visit T7). Randomized patients will return for clinic visits at Week 4 (Visit T2), Week 8 (Visit T3), Week 12 (Visit T4), Week 24 (Visit T5), Week 36 (Visit T6), and Week 52 (Visit T7).

Patients on an average daily dose of simvastatin 40 mg will be scheduled for the additional Visit T4.1 (Week 16) and T5.1 (Week 28) for clinical safety laboratory evaluations specifically to monitor changes in creatine phosphokinase (CPK) and liver function tests (LFTs). On Visit T4.2 (Week 20, phone only), and T5.2 (Week 32, phone only), these patients will be monitored for AE and SAE occurrences.

Patients who withdraw from investigational medicinal product (IMP) treatment will be asked to continue to be followed for safety using the protocol-specified visit schedule and

procedures. For details of study assessments, see Appendix 1: Schedule of Events (Patient Visit Schedule).

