5.4.2 Adverse Events of Special Interest

Adverse events of special interest (AESI) will be identified based a pre-defined list of prefer terms provided by the sponsor (Appendix 2).

AESI will be presented in a listing and summarized by SOC, PT and treatment group.

In addition to adverse events, AESI is also being evaluated based on safety lab parameters. The details are provided in 5.4.6.

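### Laboratory summaries have no dose-linked stop while adverse events stop 30 days after the last dose, and no on-treatment laboratory version is planned

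*SAP*

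**What the plan says.** SAP 3.2 puts both kinds of data into one endpoint: "The primary safety endpoint for this study is general safety, which includes adverse events (AEs), clinical safety laboratories", among other assessments. The counting windows then differ.

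- **Adverse events (SAP 3.2.1).** Treatment-emergent events are "defined as AEs that begin or worsen after the first dose of IMP until 30 days after last dose of IMP". SAP 5.4.5 likewise summarizes adjudicated cardiovascular endpoints only when they are treatment-emergent.
- **Laboratory values by visit (SAP 3.2.2).** "Observed values and changes from baseline will be summarized for all post-baseline study visits".
- **Abnormality percentages (SAP 5.4.6).** These are "summarized at each time point (i.e., including baseline and post-baseline time points) for each laboratory parameter", and unscheduled values count.
- **Laboratory thresholds of special interest (SAP 5.4.6).** "All post-baseline lab values are being considered". SAP 5.4.2 ties these to the event terms: "In addition to adverse events, AESI is also being evaluated based on safety lab parameters".

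SAP 5.4.6.1 to 5.4.6.4 add no stop. Off-drug values are collected by design. SAP 4.2 states: "Patients who withdraw from investigational medicinal product (IMP) treatment will be asked to continue to be followed for safety". The note under the schedule of events (Protocol Appendix 1, SAP Appendix 1) includes safety laboratories for those who return to clinic. Patients followed only by telephone give none (Protocol 10.3.1). An on-treatment cut-off does exist in SAP 5.3.4, at last dose plus 7 days, but for efficacy parameters only.

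**The concern.** The same finding is handled in two ways. A CK or ALT rise 60 days after the last dose enters the laboratory table of special interest. Recorded by the investigator as a new event on that date, it is not treatment-emergent. The SAP gives no reason for the difference.

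The larger consequence is for by-visit means and percentages. If a drug effect on a laboratory parameter reverses after stopping, each off-drug patient still attending pulls the active-arm value at that visit toward placebo. Laboratory safety is part of the primary endpoint, and later visits carry the long-term message of the study. As planned, the report would contain no laboratory estimate that matches the adverse-event window.

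**Working it through.** **Plan's own exposure figures (SAP 4.4).** Dropout is 7.5% at 6 months and 10.0% at 12 months, with 1300 and 650 patients.

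- 1300 × 0.925 = 1202.5 (stated 1,202); 1300 × 0.90 = 1170 (stated 1,170)
- 650 × 0.925 = 601.25 (stated 601); 650 × 0.90 = 585 (stated 585)

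The figures reproduce. They bound the planned off-drug share at 7.5% and 10%.

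**By-visit means.** Let d be the share off drug and r the share of those patients who still give laboratory samples. The documents do not give r, so it runs from 0 to 1. The off-drug share of the values at a visit is m = d·r / (1 − d + d·r). If the effect reverses fully, the fraction of it lost is m.

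| r | 6 months (d = 0.075) | 12 months (d = 0.10) |
|---|---|---|
| 0 | 0% | 0% |
| 0.25 | 2.0% | 2.7% |
| 0.50 | 3.9% | 5.3% |
| 0.75 | 5.7% | 7.7% |
| 1 | 7.5% | 10.0% |

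**Off-drug time.** Assume stopping is uniform within each half-year.

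- Mean off-drug share of follow-up = (0.0375 + 0.0875)/2 = 6.25%.
- Share more than 30 days (0.986 months) after the last dose: [6 × 0.0375 + 5.014 × 0.0854]/12 = 5.4%.

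**Ever-crossing threshold counts.** Assume constant hazards, an on-drug rate twice background, an off-drug rate equal to background, and r = 1. The background risks p are borrowed from the adverse-event range in SAP 4.4 (0.5% and 13.6%).

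- All values, active arm: 1 − (1 − p)^(2 × 0.9375 + 0.0625) = 1 − (1 − p)^1.9375. Placebo: p.
- Cut-off at last dose plus 30 days, active arm: 1 − (1 − p)^(2 × 0.9375 + 0.0081) = 1 − (1 − p)^1.8831. Placebo: 1 − (1 − p)^0.9456.

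| Background | Window | Active | Placebo | Ratio | Difference | Active patients |
|---|---|---|---|---|---|---|
| 0.5% | all values | 0.966% | 0.500% | 1.93 | 0.466% | 12.6 |
| 0.5% | +30 days | 0.939% | 0.473% | 1.99 | 0.467% | 12.2 |
| 13.6% | all values | 24.7% | 13.6% | 1.81 | 11.1% | 320.6 |
| 13.6% | +30 days | 24.1% | 12.9% | 1.86 | 11.2% | 312.8 |

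The cut-off changes the ratio by about 0.05. Simple time-weighting agrees: 2 × 0.946 + 1 × 0.054 = 1.95. Late values raise the patient counts and never lower them.

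**Simvastatin 40 mg patients.** SAP 5.4.6.1 and 5.4.6.2 plan separate liver and CK tables for patients ever on that dose or higher. The SAP's summary of changes (item 10) says these patients were withdrawn from study treatment under Amendment 5. Their event tables (SAP 5.4.4) use treatment-emergent events; their laboratory tables have no stop. Their off-drug share is not bounded by 10%, and their number is not given.

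**The case against.** Using all values is stated openly and is a legitimate treatment-policy summary. It can detect delayed effects, and the protocol deliberately keeps patients under laboratory follow-up after stopping. This stands, and it is why the planned tables should remain.

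An on-treatment table has a bias of its own. Protocol 11.1.6.3.1 to 11.1.6.3.4 link withdrawal from study drug to liver tests, renal function, hemoglobin and CK. Late on-treatment means therefore lose patients who stopped because their values worsened, and harm can be understated that way too. This also stands. It argues against replacing the planned tables, not against a second version beside them. SAP 5.3.4 follows the same pattern for lipids, with on-treatment as a sensitivity analysis.

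The upper bounds need every off-drug patient to attend and the effect to reverse fully. If dropout in SAP 4.4 means leaving the study, or patients move to telephone follow-up, the loss can be zero. Hence a range rather than a figure.

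A reader might infer that the all-values rule in SAP 5.4.6 itself dilutes the threshold results. It does not do so materially: in an ever-crossing count, a later normal value cannot cancel an earlier abnormal one. A reader might also convert the dilution into mg/dL or standard errors for uric acid or hemoglobin. The protocol synopsis reports only small mean shifts in those parameters, with no effect size, standard deviation or statement that they reverse, so the documents do not support such figures.

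**Conclusion.** The difference in windows is real and unexplained, but its effect is modest. By-visit means may understate a fully reversible effect by 0 to 7.5% at 6 months and 0 to 10% at 12 months. By-visit abnormality percentages mix on-drug and off-drug values in the same way. This rests on the plan's dropout rates, full reversal, and an unknown attendance share.

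Threshold counts barely change, given constant hazards and uniform stopping. Their remaining fault is that they cover a longer risk period than the event-term counts of special interest. To say that the two cannot be compared at all would go too far: they are separate views that would differ in ascertainment even with equal windows, and no planned analysis compares their rates.

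The simvastatin 40 mg tables are where the off-drug share could be largest, but the documents do not allow it to be sized. Overall this is a cheap improvement, not an error that invalidates the laboratory analysis.

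**What to change.** Keep the all-post-baseline tables as planned. In SAP 5.4.6 to 5.4.6.4:

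- State the counting window for each laboratory summary.
- Add a parallel on-treatment version, from first dose to last dose plus 30 days to match treatment-emergent events. It should cover the by-visit change tables, the by-visit abnormality tables and the laboratory tables of special interest, including those for simvastatin 40 mg patients.
- Flag values after that stop in the listings.
- Note that the two versions are to be read together, because stopping can depend on the laboratory values.

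The cost is SAP wording, one further run of existing table programs, and a second set of tables to review. No new data are needed.
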